In most of Malawi, including in Neno District, the usual care procedure for addressing depression is for patients who self-present with significant symptoms such as psychosis, suicidal ideation or attempt or potential harm to others receive a referral either to a mental health clinical officer or nurse within the district (in Neno District there are three), or else to a mental health specialist at a regional hospital. Due to the limited supply of mental health clinicians in Neno District, those with comorbid conditions such as schizophrenia or more complex mood disorders such as bipolar disorder are prioritized for immediate intervention. Of those who presently receive treatment for overt mood disorders, treatment typically comprises pharmacotherapy—including fluoxetine or amitriptyline for depressive symptoms with individual counseling if time and staff is available. There is currently no system-wide model in IC3 or primary services for screening for depression. However, Neno District has begun

screening and treatment for peripartum depression at one antenatal clinic—a system separate from the IC3 system which is the focus of this work. The inclusion of depression screening and psychoeducation, features of the control arm of this study, represent modest enhancements of the existing system from which the full IC3 model will be introduced.

With regard to IC3, services are condition-specific. To provide an example: HIV/AIDS is the most common chronic care condition treated at IC3, constituting approximately 70% of enrollees. Patients receiving antiretroviral therapy attend clinic every three to six months for evaluation (e.g. screening, adherence, viral load) and are provided with a necessary supply of antiretroviral medications until their scheduled return date. Patients with non-suppression, missed appointments or poor adherence are evaluated on a monthly basis. Non-communicable disease (NCD) patients attend clinic every 3 months with 1-month appointments with poor disease control or missed appointments. They are screened for comorbid disease (e.g. HIV, tuberculosis [TB], other NCDs) and provided with necessary supply of medications to their scheduled return date.

Treatment: IC3D

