Overall health. A health profile will be generated for each individual enrolled in IC3D, using the EQ-5D-5L⁶⁶—previously validated in Malawi.⁶⁷ This survey determines patients' overall health at time of interview and offers a cross-walk to quality-adjusted life years (QALYs).⁶⁸

Secondary Outcomes

Secondary outcomes will constitute those measuring *indirect* benefits and costs of treatment. Indirect benefits will be incorporated into cost-effectiveness estimates by internalizing improvements among comorbid conditions such as HIV and hypertension, as well as reduced household burden of care.

ART adherence. ART adherence will be measured in terms of whether HIV+ enrollees have returned to an IC3 for antiretrovirals (ARVs) within the past three months or else defaulted, an approach considered more reliable than self-reports.^{69,70} This interval overlays

with clinical protocols throughout Malawi in terms of the duration for which ARVs are supplied.

Viral load. Viral load will be measured as part of HIV+ patients' clinical assessment pre-intervention, post-intervention, 6- and 12-month follow-up, consistent with ongoing care at IC3s. This is considered a key metric for determining treatment plans and is highly sensitive to compliance with prescribed ART regimens.⁷¹

HIV disease staging. Staging will be evaluated every three months among HIV+ enrollees, consistent with IC3 visits. This approach to tracking disease progression is commonly used in low-resource settings.⁷²

Chronic care outcomes. Chronic care outcomes on hypertension, type-2 diabetes, and epilepsy will be abstracted from electronic medical records. Systolic blood pressure and adherence to antihypertensive medication (measured by adherence to clinic visits with medication dispensing) will be measured among those with hypertension. Among those with type-2 diabetes, adherence to quarterly visits with medication dispensement and A1C (or random blood sugar) levels will be abstracted. Among those with epilepsy, we will catalog number of reported seizures in past quarter, and adherence to antiepileptics as measured by quarterly medicine pickups.

Household burden of care. Lastly, household burden of care will be evaluated with household members using a locally-adapted version of the Burden Assessment Schedule (BAS),¹⁵ previously implemented by the team.¹⁷ The survey assesses dimensions of emotional and functional burden of care, including missed work, guilt and worry.

Mediators and Moderators

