The data from the trial will be analyzed using a generalized linear mixed model framework, which is standard for stepped-wedge cluster designs.^{87,88} The patients participating form an open cohort with repeated measures, as it will be possible to link each patient taking a PHQ-9 screening and any subsequent exams over time. The models will be at the patient-level, nested within clinic-months and clinics. The primary outcomes are: (i) prevalence of depression; (ii) depression severity (PHQ-9 score) conditional on having depression; (iii) WHODAS score conditional on having depression; and (iv) utility score (0 to 1) from the EQ-5D-5L. The first outcome is a dichotomous event for if the patient has depression or not, while the remaining outcomes are treated as continuous. For the principal analysis of the trial, we used the “complete” stepped-wedge of data from months 1 to 18; long-term follow-up will constitute a secondary analysis.

We specify the following model for patient $i = 1, \dots, N$ in clinic $j = 1, \dots, J$ at time period $t = 1, \dots, T$:

$$y_{ijt} \sim F(g(\eta_{ijt}))$$

$$\eta_{ijt} = \mu + x'_{ijt}\beta + z'_{jt}\gamma + \delta D_{(i)jt} + \theta_i + \alpha_j + \phi_{jt} + \tau_t$$

where y_{ijt} is the outcome, $F(\cdot)$ is an appropriate likelihood and $g(\cdot)$ is a suitable link function, x_{ijt} and z_{jt} are respectively patient and clinic level covariates, τ_t are monthly fixed effects, and $\theta_i \sim N(0, \sigma_\theta^2)$, $\alpha_j \sim N(0, \sigma_\alpha^2)$, and $\phi_{jt} \sim N(0, \sigma_\phi^2)$ patient-, clinic-, and clinic-time random

effects term. We will take both intention to treat (ITT) and per protocol approaches. For the ITT analysis, the variable D_{jt} is an indicator equal to one if cluster j is in the intervention state at time t and zero otherwise, thus δ represents our estimated treatment effect. For per protocol analysis D_{ijt} will be a patient-level variable equal to one if the clinic was in the intervention state and the patient completed the treatment as defined above, and zero otherwise. For dichotomous outcomes, we will use a Bernoulli distribution with logistic link function, for continuous outcomes a normal distribution with identity link function. The same models will be used for secondary outcomes.

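### The three-month default rule for ART adherence conflicts with the three-to-six-month visit and supply interval stated elsewhere in the protocol

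*Protocol*

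**What the plan says.** Protocol, Secondary Outcomes, ART adherence: the outcome is whether HIV+ enrollees "have returned to an IC3 for antiretrovirals (ARVs) within the past three months or else defaulted". The reason given for three months is that it agrees "with clinical protocols throughout Malawi in terms of the duration for which ARVs are supplied".

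Protocol, Treatment: Usual Care, describing IC3: "Patients receiving antiretroviral therapy attend clinic every three to six months for evaluation", and they "are provided with a necessary supply of antiretroviral medications until their scheduled return date". There is one exception: "Patients with non-suppression, missed appointments or poor adherence are evaluated on a monthly basis". The same paragraph gives NCD patients a three-month interval.

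Other places mention quarterly contact. Under HIV disease staging: "Staging will be evaluated every three months among HIV+ enrollees, consistent with IC3 visits". The Treatment: IC3D section refers to PHQ-9 at quarterly visits, the costing section counts four IC3 visits a year, and the SAP appendix describes the screening period as quarterly. None of these says how often ARVs are collected.

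On analysis, the protocol says "For dichotomous outcomes, we will use a Bernoulli distribution with logistic link function" and "The same models will be used for secondary outcomes". The SAP applies the primary-outcome procedure to secondary outcomes, with changes suited to each outcome, and does not define ART adherence. Neither document gives a grace period, an alternative definition of default, or a check schedule for this outcome.

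**The concern.** A look-back window works as a default measure only if it is at least as long as the supply. For a patient given more than three months of ARVs, part of every cycle lies outside the window although the patient holds drug and has missed nothing. Recorded default would then mix true default with a product of the visit schedule.

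The error could also differ between conditions. The Usual Care text ties monthly evaluation to non-suppression, missed appointments or poor adherence. If the intervention improved adherence, patients might move to longer intervals and be scored as defaulted more often under intervention. ARV pick-ups at extra depression-care visits, which the documents do not describe, could act the other way.

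HIV accounts for about 70% of IC3 enrollees, and the Introduction names medication adherence as a route from depression treatment to better physical health. The measure therefore carries weight, although it is only one secondary measure; the Study Design section lists adherence as a process of care.

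**Working it through.** The documents state no misclassification rate for this outcome, so there is no figure to reproduce.

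**Inputs.** Window W = 3 months (ART adherence). Interval L = 3 to 6 months, or 1 month for the exception group (Usual Care). Timing of checks: not stated. Share of enrollees on each interval: not stated.

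**1. Evenly spread checks (assumed).** An on-time patient is outside the window for L − 3 months of each cycle, so the share of checks scored as default is max(0, (L − 3)/L).

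| L (months) | Calculation | False default |
|---|---|---|
| 1 or 3 | 0 | 0% |
| 4 | 1/4 | 25% |
| 5 | 2/5 | 40% |
| 6 | 3/6 | 50% |

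**2. Fixed schedules.** Here every possible starting point relative to pick-up is taken, and exactly three months counts as inside the window.
- Quarterly checks: 0% at L = 3; 0 to 25% at L = 4; 20 to 40% at L = 5; 0 to 50% at L = 6. The 0% at six months needs checks exactly at pick-up and exactly three months later. If the boundary day is not counted as adherent, that case becomes 50%.
- Six-monthly checks at L = 6: each check falls at the same point of the cycle, so the rate is 0% if that point is within three months of pick-up and 100% if it is later.

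**3. Overall rate.** If a share q of on-time patients is on six months and the rest on three, evenly spread checks give 0.5q: 12.5% at q = 25%, 25% at q = 50%.

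**4. Effect on the treatment contrast.** All inputs are assumed: evenly spread checks, every true default detected, half of enrollees on six months unless stated, true default 20% control and 15% intervention. The true difference is 5.0 points, OR = (0.15/0.85)/(0.20/0.80) = 0.71.
- (i) Interval unrelated to default risk. Recorded risk = d + (1 − d) × 0.25, giving 40.0% vs 36.25%; difference 3.75 points, OR 0.85.
- (ii) No true default among six-month patients (so 40% vs 30% among the rest). Recorded risk = d + 0.5 × 0.50, giving 45% vs 40%; difference 5.0 points, OR 0.81.
- (iii) As (ii), with the six-month share at 60% under intervention: 45% vs 0.15 + 0.5 × 0.60 = 45%; difference 0, OR 1.00.
- (iv) As (ii), with the share exposed to the error at 40% under intervention: 45% vs 0.15 + 0.5 × 0.40 = 35%; difference 10.0 points, OR 0.66.

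**5. Does the odds ratio always move towards 1?** No. Adding the same amount to both risks pulls it towards 1 only if the risks come nearer 50%. Under model (ii) with true default 45% vs 40%, OR = (0.40/0.60)/(0.45/0.55) = 0.815. Adding 25 points gives 70% vs 65%, OR = (0.65/0.35)/(0.70/0.30) = 0.796, further from 1. This needs very high default (90% vs 80% outside the six-month group) and only shows that no general rule exists.

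These odds ratios are marginal; the conditional ones from the planned mixed model would differ.

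**The case against.** The strongest reply is that the conflict may be one of wording only. The Usual Care paragraph is background, introduced as an example, while staging, treatment review and costing all speak of quarterly contact. If every HIV+ enrollee collects ARVs quarterly, the rule misclassifies no on-time patient. That reading stays open. It does not remove the conflict, because none of the quarterly statements concerns ARV collection. The Usual Care paragraph describes the trial's own platform and separates ART patients from NCD patients by interval. On either reading one passage needs correcting.

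It is also fair that the illustrations rest wholly on assumed inputs, and that the Usual Care text gives no rule for moving a patient to a six-month interval. They show that the bias cannot be signed. They do not estimate it.

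Three stronger readings are tempting. A reader might infer that 50% is the most that can go wrong; it is the ceiling for evenly spread or quarterly checks, and the schedule is not stated. A reader might infer simple dilution, with the odds ratio always pulled towards 1; steps 4 and 5 show otherwise. A reader might infer that the adherence result is known to be biased; without the mix of intervals, the documents do not show that.

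Finally, scoring against each patient's own return date is not neutral. Time to a possible default would then depend on the interval, so if intervals lengthen under intervention, the opportunity to be scored as defaulted falls there. This stands, and the fix has to allow for it.

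**Conclusion.** The contradiction is certain and its consequence is conditional. If the three-to-six-month interval holds, the rule scores some on-time patients as defaulted: 25%, 40% and 50% of checks at four, five and six months with evenly spread checks, 0% to 50% with quarterly checks depending on timing, and up to 100% with six-monthly checks late in a six-month cycle. If all enrollees collect every three months, the error is 0%. The documents settle neither the check schedule nor the share on each interval, so the size and direction of any bias in the treatment effect are unknown. Only the ART adherence measure is affected; primary outcomes and viral load are not. The point is worth correcting before analysis, but it does not threaten the trial's main conclusions.

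**What to change.** Reconcile the Usual Care and ART adherence passages in the outcome definition.

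- Score default as failure to return by the scheduled return or supply-end date in force at the check, plus one fixed, pre-stated grace period applied identically in control and intervention periods. For on-time patients this gives 0% false default at every interval.
- State the check schedule for this outcome.
- Report the distribution of scheduled intervals by condition, and keep the three-month definition as a sensitivity analysis, because own-date scoring makes time to a possible default depend on the interval.
- If supply is in fact three-monthly for all enrollees, correct the Usual Care text and keep the window.

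The cost is wording plus extraction of the scheduled return date or days supplied. The Primary Outcomes section lists pharmacy and chart data in general but does not confirm these fields. Intervals can change over time, so the date in force at each check is needed, and default will be detected later in patients with longer supply. No change to visit schedules or care is proposed.

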Provider experience: In Year 5, we will interview up to 10 providers including clinical officers who prescribed ADT, as well as psychosocial counsellors who led PM+ sessions. In addition to discussing perceived strengths and weakness of the intervention and its implementation, we will also discuss the training and supervision process, as well as provider job satisfaction and burnout.

Patient experience: A random sample of 20 participants (10 male, 10 female) will be interviewed after their final study assessment to assess their experiences with the intervention – including logistical aspect of participation, impact on personal mental health and wellbeing, as well as changes in relationships at the household level.

Sample Size

We assumed $n=30$ enrollees per facility (total $n=420$) during each three month “step”, based on an estimated 10% depression prevalence in Malawi.^{7,84} We further assumed loss to follow-up of 15%, based on intervention trials we have conducted in similar settings.^{11,85}

The power calculation is based on the model described in the analysis section (see below) and a two-sided null value of no effect.⁸⁶ To indicate the precision of the study design, we report “minimum detectable effect” sizes across the range of our primary outcomes at 80%

power, with a type I error rate of 0.05, and conservative intraclass correlation coefficient (ICC) of 0.05, a cluster autocorrelation coefficient (CAC) of 0.80, and an individual autocorrelation coefficient (IAC) 0.80. Table 2 reports these effect sizes.

Analysis of Intervention Effects

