All models will be estimated using restricted maximum likelihood using the R package lme4. We will report point estimates, confidence intervals, and p-values but not make any claims of “statistical significance” given recent strong arguments against doing so.⁸⁹ P-values will be based on the null hypotheses $H_0: \delta = 0$ versus the two-sided alternatives $H_1: \delta \neq 0$ in each of the models. Given there are multiple primary outcomes, we will adjust reported p-values for multiple testing using a stepdown method, which provides an efficient means of controlling the family-wise error rate.⁹⁰ We will derive the exact distributions of the test statistics to perform the stepdown procedure using a (pseudo-)permutation test approach, by re-randomizing clusters to different sequences in the stepped-wedge design 100,000 times.⁹¹ This method ensures appropriate control of the family-wise error rate and avoid potential biases resulting from small numbers of clusters.

Cost and cost-effectiveness analysis

The research team will employ time-driven activity-based costing (TDABC) to gather program costs before (Year 1) and after (Year 4) intervention roll-out. TDABC is a gold

standard, patient-centered approach: It begins by studying flow of patients through the health system, and then measuring human and other resources expended. Baseline costs, gathered in Y1, will assess cost of care as usual for individuals utilizing IC3s. A cycle of care will be annualized as four quarterly IC3 visits, inclusive of testing and labs, according to diagnosis. Itemized expenditures will be accrued from PIH's financial software system.⁹² To assess economic costs, such as subsidized ARVs by PEPFAR, we will use external cost sources such as management Science for Health's International Medical Product Price Guide (MSH-IMPPG).⁹³ As the cost comparator, we will replicate the cost exercise in Year 4, when depression care is operating at scale, again tracing individuals according to service type—now including depression care.

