The parameters of interest are δ_k , which are a (log) odds-ratio for the prevalence outcome and a mean absolute difference in score for the three individual-level outcomes. We will take both intention to treat (ITT) and per protocol approaches for the individual level outcomes. For the ITT analysis, the variable D_{jt} is an indicator equal to one if cluster j is in the intervention state at time t and zero otherwise. Thus, δ represents our estimated treatment effect. For the per protocol analysis, D_{ijt} will be a patient-level variable equal to one if the clinic was in the intervention state and the patient completed the treatment as defined above, and zero otherwise. As we describe below, we will use a randomisation test method to derive exact inferential statistics (p-values and confidence intervals) for the parameters of interest.

Outcomes 2-4 described above are only recorded for those who screen positive for depression at their scheduled visit. Thus, the data do not all cover the full patient population: data for outcomes 2 to 4 are a subset of those for outcome 1. Based on this, we anticipate the data to be normally distributed. However, we will test this assumption by examining QQ plots and conducting KS (Kolmogorov Smirnov) and SW (Shapiro Wilk) tests. In the event the normality assumption is violated, we will consider an alternative specification, such as a two-part semi-continuous model.

Statistical Inference

All models will be estimated separately using restricted maximum likelihood, using the R package lme4. We will report point estimates, confidence intervals, and p-values but not make any claims of "statistical significance", given recent strong arguments against doing so [2].

P-values will be based on the null hypotheses $H_0: \delta_k = 0$ versus the two-sided alternatives $H_1: \delta_k \neq 0$ in each of the models defined above. Given that there are multiple primary outcomes, we will adjust reported p-values for multiple testing using a cluster-based stepdown method, which provides an efficient means of controlling the family-wise error rate [18]. The full methodology is described elsewhere, but we describe it here briefly.

Let there be P hypotheses to be tested H_1, \dots, H_P with associated test statistics T_p . We let the ordered test statistics be:

$$T_{[1]} \geq T_{[2]} \geq \dots \geq T_{[P]}$$

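### The protocol's 80% power is stated at a type I error of 0.05 with no multiplicity input, but primary p-values are adjusted over four outcomes; if 0.05 is per outcome, power per outcome is about 62-75%

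*Protocol*

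**What the plan says.** The protocol's Sample Size section gives an MDE for each primary outcome, with power set to 80%. It describes the settings as follows: "power, with a type I error rate of 0.05, and conservative intraclass correlation coefficient (ICC) of 0.05". Besides these it assumes "a cluster autocorrelation coefficient (CAC) of 0.80, and an individual autocorrelation coefficient (IAC) 0.80", 30 enrollees per facility per three-month step, and 15% loss to follow-up. The test is against "a two-sided null value of no effect". On the basis of the calculation the section says: "The power calculation is based on the model described in the analysis section (see below"). The values are in a table ("Table 2 reports these effect sizes"), which is not in the text available for this review.

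The protocol's Analysis of Intervention Effects section names four primary outcomes: depression prevalence, PHQ-9 severity, WHODAS score and EQ-5D utility. It then says: "Given there are multiple primary outcomes, we will adjust reported p-values for multiple testing using a stepdown method". The SAP, under Statistical Inference, agrees: "we will adjust reported p-values for multiple testing using a cluster-based stepdown method". It describes a procedure that compares the largest statistic with the permutation distribution of the largest in the family, drops that hypothesis if it is rejected, and repeats on the remainder. The SAP also plans 95% confidence intervals with family-wise coverage. It has no sample-size section.

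**The concern.** The power statement and the planned test are not connected. The inputs listed for the MDEs include no divisor for the number of outcomes, no correlation between outcomes and no simulation of the stepdown. The model on which the calculation rests has one outcome and one treatment effect. At its first step, however, the planned test compares the largest of four statistics with a critical value well above 1.96.

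The MDEs are the plan's only statement of what the trial can detect. If they were computed outcome by outcome at 0.05, they describe unadjusted tests and intervals, while the trial will report adjusted ones. A reader who sets an unremarkable adjusted p-value beside the 80% figure would take it as stronger evidence against an effect of that size than it is. The family-wise intervals will also be wider than the MDEs suggest.

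**Working it through.** **Inputs from the documents.** Two-sided type I error 0.05; power 80%; four primary outcomes; max-statistic stepdown.

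**Assumptions.** The 0.05 applies to each outcome. Test statistics are normal with equal pairwise correlation ρ, which the documents do not give, so ρ runs from 0 to 0.9. The test is correctly sized, with the critical value at the 95th percentile of the largest absolute statistic. The small number of clusters (14) is not modelled.

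**The plan's own figure.** The MDE values cannot be reproduced without Table 2, the SDs and the baseline rates. The definition can be. At two-sided 0.05 and 80% power an MDE is 1.960 + 0.842 = 2.802 standard errors, and Φ(2.802 − 1.960) = Φ(0.842) = 0.80. The checks below stay in standard-error units, so they do not depend on the ICC, the autocorrelations or the cluster sizes.

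**One outcome responds.** Power ≈ Φ(2.802 − c₄), where c₄ is the critical value for the largest of four.
- ρ = 0: c₄ = 2.491, and Φ(0.311) = 0.62.
- ρ = 0.9: c₄ = 2.236, and Φ(0.566) = 0.71.

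For comparison, Bonferroni at 0.05/4 = 0.0125 gives 0.619.

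**All four at their MDE.** The full stepdown was simulated, with the family shrinking after each rejection.

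| ρ | c₄ | One responds: power | All four respond: per outcome | At least one | All four |
|---|---|---|---|---|---|
| 0 | 2.49 | 62% | 73% | 98% | 38% |
| 0.3 | 2.48 | 63% | 72% | 93% | 47% |
| 0.5 | 2.44 | 64% | 72% | 90% | 53% |
| 0.7 | 2.38 | 66% | 73% | 86% | 60% |
| 0.9 | 2.24 | 71% | 75% | 82% | 69% |

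With two or three outcomes responding, per-outcome power is 65-74%. It is below 80% in every scenario run.

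**MDE needed to restore 80% per outcome.**
- One outcome responds: the ratio is (c₄ + 0.842)/2.802. At ρ = 0 this is 3.333/2.802 = 1.19; at ρ = 0.9 it is 3.078/2.802 = 1.10. The increase is 10-19%.
- All four respond: by simulation of the full stepdown the ratio is 1.06 to 1.08, an increase of about 6-8%.

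**Why no MDE in SD units is offered.** For a continuous outcome, with the plan's correlations, six periods and an assumed 3, 3, 3, 3, 2 split of clinics, the unadjusted MDE is 0.139 SD if the same 30 people are measured in every period without loss. It is 0.228 SD if 30 × 0.85 = 25.5 new people are measured each period. The open cohort lies somewhere between, and neither figure represents the prevalence outcome.

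**The case against.** The strongest reply is that the text never says 0.05 is per outcome. The calculation refers to the analysis section, which contains the stepdown, and Table 2 might carry a label that settles the matter. A reader might infer that the stated MDEs are miscalculated. The documents do not support that, because no stated number has been shown to be wrong. What stands against the reply is that a family-wise calculation would need an input that is not listed, and that the section ties power to a single-outcome model.

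A second reply is that power need not mean per-outcome power. A reader might infer that the design simply lacks 80% power. That goes too far: if all four outcomes are at their MDE, at least one is detected in 82-98% of trials. But the protocol does not claim at-least-one power, and an MDE quoted for each outcome describes that outcome. At-least-one power is also not secure if fewer outcomes respond: with two responding it runs from 86% at ρ = 0 to 77% at ρ = 0.9.

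Third, 62% is the least favourable case, and the SAP expects benefit on prevalence, severity and quality of life together. This is fair. It makes the 72-75% range the more relevant one if the intervention works as hoped, and it is why a general MDE increase of 19% would overstate the cost.

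Fourth, the MDEs are offered as an indication of precision, and both documents renounce claims of statistical significance. This lowers the consequence. The mismatch remains, because adjusted p-values and family-wise intervals are what will be reported.

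**Conclusion.** The power statement does not match the planned test as written. On the natural reading that 0.05 is per outcome, the 80% is an unadjusted figure. Per-outcome power at the stated MDEs under the stepdown is about 62-71% if one outcome responds and about 72-75% if all four do. This rests on normal, equally correlated statistics and a correctly sized test. If Table 2 was in fact computed family-wise, the shortfall disappears and only the missing statement remains.

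Severity is moderate to minor. Family-wise error control, the effect estimates and the patient numbers are unaffected. One related point needs clarifying separately: the SAP writes the critical value as the 1 − α/2 quantile of the largest statistic. If that statistic is an absolute value, power would be lower than shown here.

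**What to change.** State in the protocol's Sample Size section whether 0.05 is per outcome or family-wise, and whether the 80% refers to a given outcome, at least one, or all four. If it is per outcome, take one of two routes:

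- Keep Table 2, label its 80% as unadjusted, and add simulated power under the planned stepdown for stated correlations and patterns of response.
- Recompute Table 2 with the stepdown built in. MDEs would rise by about 10-19% if one outcome responds and about 6-8% if all four do.

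The simulation should use the planned permutation test with 14 clinics and the SAP's binomial model for prevalence. The cost is one calculation and one sentence or revised table. The stated figures become somewhat less favourable; no extra patients and no design change are needed.
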